3.7 Treatment assignment and treatment groups

This is an open label, single arm study.

Treatment group at the completion of AS0008 (presented as ‘BKZ 160mg’ or ‘BKZ 320mg’) and an overall ‘BKZ Total’ column will be used to summarize data in AS0009.

The endpoints assessing maintenance of ASAS response over time will be summarized by treatment sequence across AS0008 and AS0009, and overall. Treatment sequences take the form ‘A/ B/ C’, where A is the treatment in the first 12 weeks of AS0008, B is the treatment from Week 12 to Week 48 of AS0008, and C is the treatment in AS0009. The eight planned treatment sequences are as follows:

- Placebo/BKZ 160mg/BKZ 160mg.
- Placebo/BKZ 320mg/BKZ 160mg.
- BKZ 16mg/BKZ 160mg/BKZ 160mg.

- BKZ 16mg/BKZ 320mg/BKZ 160mg.
- BKZ 64mg/BKZ 160mg/BKZ 160mg.
- BKZ 64mg/BKZ 320mg/BKZ 160mg.
- BKZ 160mg/BKZ 160mg/BKZ 160mg.
- BKZ 320mg/BKZ 320mg/BKZ 160mg.

Safety summaries including AS0009 data only will be presented by treatment group at the completion of AS0008 and overall. Safety summaries including data from both AS0008 and AS0009 combined will be presented for 'BKZ 160mg', 'BKZ 320mg', and 'BKZ Total', based on the SS for AS0009. Subjects who took bimekizumab 320mg during AS0008 will contribute to all three columns. Subjects who did not take 320mg in AS0008 will contribute to the 'BKZ 160mg' and 'BKZ Total' columns. The combined summaries will present data from AS0008 and AS0009 for the subjects who were enrolled in AS0009. The AS0009 only summaries will include only data collected in AS0009 (unless otherwise stated).

Subjects will be summarized and listed based on the actual/received treatment or the planned treatment for different analysis sets as follows:

- ES: planned treatment.
- SS and Sub-populations: actual treatment.
- FAS: planned treatment.

For actual and planned treatments in AS0008, the data will be used directly from the AS0008 analysis database without any rederivation of treatment assignments in each period.

In AS0009 it will be assumed that all subjects received the correct treatment as the dose level of bimekizumab is the same for all subjects and throughout the study (160mg). If a subject missed a dose at AS0008 Week 48, they will also be considered to have received the planned treatment. Thus for all subjects in AS0009 the actual treatment will be the same as the planned treatment.

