3.10 Changes to protocol-defined analyses

The following changes have been made to the protocol-defined analyses:

- Change from AS0009 EV for safety variables will no longer be presented, since the EV assessment is made after 36 or 48 weeks of bimekizumab treatment and there is unlikely to be any further important change.
- Change from AS0008 Baseline and AS0009 EV for laboratory variables will not be presented, due to a change in laboratory vendor between AS0008 and AS0009. Laboratory Baseline has been defined as the earliest value in AS0009 at or prior to AS0009 Week 12.
- Summaries of ASAS40, ASAS20 and ASAS5/6 response at each post-AS0008 Baseline visit have been added for subjects who were responders at AS0008 Week 12. These summaries include all post-AS0008 Baseline visits through to AS0009 Week 208, for subjects in the FAS for AS0009, and will be used to assess maintenance of response.
- The protocol describes the FAS as consisting of all enrolled subjects who receive at least 1 dose of IMP and have a valid measurement for at least 1 efficacy variable at AS0009 study entry. This has been updated to include all subjects in the ES who received at least one dose of study medication in AS0009 and have a valid measurement for at least one efficacy variable at a scheduled visit (excluding SFU visits) after AS0009 EV. This was updated in order to identify subjects who have had assessments during AS0009 and which contribute to any of the efficacy analyses.
- Summaries by randomized treatment in AS0008 will not be produced, as subjects will have been on a constant dose of bimekizumab 160mg or 320mg for at least 36 weeks prior to AS0009 entry. Maintenance of response displays will be split by treatment sequence across AS0008 and AS0009. Safety displays using AS0008 information will incorporate exposure in AS0008.
- The protocol defines subgroups based on ‘Concomitant non-steroidal anti-inflammatory drug (NSAID) status at AS0009 entry. This has been updated to ‘Concomitant NSAID status at start of AS0008’.
- The protocol stated that all safety analysis would be performed for both Sub-populations; instead only key safety analyses will be repeated by Sub-population as identified in [Section 10](#). These analyses will be performed only in the event that the number of subjects receiving rescue medication is $\geq 10\%$ of the total number of subjects in the SS.

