10.1 Extent of exposure

Study medication duration will be calculated for each of the following using the imputation rules in [Section 4.2.4](#) for partial treatment end dates:

- Total bimekizumab duration: Between the first dose of bimekizumab in AS0008 and last dose of bimekizumab in AS0009.
- Total duration on bimekizumab 160mg: Between the first and last dose of bimekizumab 160mg (in AS0008 or AS0009).

- Duration on bimekizumab 320mg: Between the first dose of bimekizumab 320mg in AS0008 and first dose of bimekizumab 160mg in AS0009 (calculated only for subjects who took bimekizumab 320mg in AS0008).
- Duration on bimekizumab 160mg in AS0009: Between the first and last dose of bimekizumab 160mg in AS0009.

The duration of exposure will be calculated as outlined in [Table 10–1](#).

Table 10–1: Study medication duration

Duration Category	Start date	End date	Study medication duration
Total BKZ duration	First dose of BKZ in AS0008	Last dose of BKZ in AS0009	End date – start date + 28 ^a
Total duration on BKZ 160mg	First dose of BKZ 160mg in AS0008 or AS0009	Last dose of BKZ 160mg in AS0009	End date – start date + 28 ^a
Duration on BKZ 320mg	First dose of BKZ 320mg in AS0008	First dose of BKZ 160mg in AS0009	End date – start date + 1
Duration on BKZ 160mg in AS0009	First dose of BKZ 160mg in AS0009	Last dose of BKZ 160mg in AS0009	End date – start date + 28 ^a
Subjects who died ^b	Start date for each option as above	Date of death	End date – start date + 1

BKZ=bimekizumab.

^a 28 days refer to one half-life of BKZ.

^b For subjects who died, the date of death will be used to replace the end date in the calculation of study medication duration only if the subject died within the dosing interval (i.e., within 28 days following the last dose [not applicable for duration on BKZ 320mg]) or if the subject died before dosing in AS0009 (for duration on BKZ 320mg). If the subject died more than 28 days after the last dose of BKZ in AS0009 the study medication duration will be calculated using the dosing interval of 28 days.

The exposure time at risk will be calculated as outlined in [Table 10–2](#).

Table 10–2: Exposure time at risk

Exposure Category	Start date	End date	Duration of Exposure
Total BKZ exposure	First dose of BKZ in AS0008	Last dose of BKZ in AS0009	Minimum of [(End date – start date + 140 ^a) +1] and (Date of last clinical contact ^b – start date + 1)

Table 10–2: Exposure time at risk

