- Serious TEAEs by treatment group at completion of AS0008 and overall, by SS Sub-population.
- All TEAEs in AS0008 and AS0009 by treatment at time of AE onset (BKZ 160mg, BKZ 320mg and BKZ Total).
- Serious TEAEs in AS0008 and AS0009 by treatment at time of AE onset (BKZ 160mg, BKZ 320mg and BKZ Total).

- All TEAEs AS0008 and AS0009 by timing of onset relative to ADAb status in AS0008 and AS0009. This will include columns for the following:
 - TEAEs starting before the first ADAb positive result in AS0008 and AS0009 (includes ADAb Categories 2b only)
 - TEAEs starting on the same date or after the first ADAb positive result in AS0008 and AS0009 (includes ADAb Categories 2b, 3b, 4b, 5b and 6b)
 - TEAEs for subjects who are ADAb negative at all time points in AS0008 and AS0009 (includes ADAb Categories 1b only)

Note that any TEAEs occurring for a subject who was ADAb positive at AS0008 Baseline will therefore all occur after ADAb positivity; such subjects will be excluded from the first column in the above table. Subjects in Category 9b (missing) will not be included in the table.

The following categories of TEAE will be summarized by MedDRA SOC, HLT and PT, by treatment group at completion of AS0008 and overall:

- TEAEs leading to study discontinuation and/or permanent withdrawal of study medication.
- TEAEs leading to permanent withdrawal of study medication.
- TEAEs with a fatal outcome.
- All TEAEs by maximum relationship.
- Serious TEAEs by maximum relationship.
- TEAEs with a fatal outcome by maximum relationship.
- All TEAEs by maximum intensity.
- Non-serious TEAEs reported by more than the reporting threshold of 5% of subjects. The cut-off will be applied before rounding on each treatment group and overall.

A further summary will be presented by treatment group at completion of AS0008 and overall displaying the frequency of TEAEs by descending frequency of PT.

An additional table will be presented by MedDRA SOC, HLT and PT, by treatment at time of AE onset (BKZ 160mg, BKZ 320mg and BKZ Total) for all TEAEs in AS0009 and all TEAEs that were ongoing from AS0008 at the time of the AS0009 EV. Ongoing TEAEs are defined as TEAEs that started prior to the AS0009 EV and continued after the first dose of study medication in AS0009.

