Summaries will be based on treatment at onset and include columns for BKZ 160mg, BKZ 320mg and BKZ Total (where BKZ Total includes all other doses, if applicable, excluding placebo). Tables will include only n and %, the denominator (i.e. N) will be as for the current tables (total number of subjects receiving at least one dose for each column)

TEAEs classified as Safety Topics of Interest and associated tables are defined in [Section 10.2.3](#).

The following AE listings will be provided based on the ES:

- Glossary table for all TEAEs (this listing will include all events in AS0008 and AS0009 for subjects that were enrolled in AS0009 [with the exception of AEs with onset during placebo treatment]).
- All AEs (this listing will include all events in AS0008 and AS0009 for subjects that were enrolled in AS0009 [with the exception of AEs with onset during placebo treatment]).
- All SAEs (this listing will include all events in AS0008 and AS0009 for subjects that were enrolled in AS0009 [with the exception of AEs with onset during placebo treatment]).
- All AEs leading to study discontinuation.
- All deaths.

The following listings will be provided based on the SS:

- Serious Infections TEAEs.
- Fungal infectious disorder TEAEs.
- Opportunistic infection (including tuberculosis [TB]) TEAEs.
- Malignant or unspecified tumor TEAEs.
- Malignant tumor TEAEs.
- Adjudicated cardiovascular TEAEs by event type.
- Adjudicated cardiovascular TEAEs by event type for major adverse cardiac events (MACE)
- Adjudicated cardiovascular TEAEs by event type for extended MACE
- TEAEs identified for potential review by the Cardiovascular Event Adjudication Committee.
- Neutropenia TEAEs.
- Suicidal ideation and behavior TEAEs
- TEAEs identified for potential review by the Neuropsychiatric Adjudication Committee.
- TEAEs adjudicated by the Neuropsychiatric Adjudication Committee.
- Inflammatory bowel disease TEAEs.
- Hypersensitivity reaction TEAEs.
- Anaphylactic reaction TEAEs
- Hepatic events TEAEs.
- Hospitalization/Emergency Room Visits.

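### In the SAP 10.2 table that pools AS0009 TEAEs with TEAEs ongoing from AS0008, the 160 mg and 320 mg columns count events by different rules, so their crude percentages cannot be compared between doses

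*SAP*

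**What the plan says.** SAP 10.2 (Adverse events) describes one additional TEAE table by SOC, HLT and PT. Its columns are dose at onset, and it is produced "by treatment at time of AE onset (BKZ 160mg, BKZ 320mg and BKZ Total) for all TEAEs in AS0009 and all TEAEs that were ongoing", meaning those carried over into AS0009 from the lead-in study. Carried-over events are defined as follows: "Ongoing TEAEs are defined as TEAEs that started prior to the AS0009 EV and continued after the first dose of study medication in AS0009". AS0008 events that resolved before then are left out.

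On presentation, the same section says "Tables will include only n and %, the denominator (i.e. N) will be as for the current tables", glossed as the "total number of subjects receiving at least one dose for each column". The Total column also takes in other bimekizumab doses; placebo is excluded. No EAIR, EAER or caution is attached.

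Four other provisions decide what each column can contain:
- SAP 3.7: all AS0009 dosing is at 160 mg. In the combined AS0008 and AS0009 summaries, "Subjects who took bimekizumab 320mg during AS0008 will contribute to all three columns".
- SAP 10.1: the 320 mg period closes when AS0009 dosing starts. "Duration on bimekizumab 320mg: Between the first dose of bimekizumab 320mg in AS0008 and first dose of bimekizumab 160mg in AS0009".
- SAP 3.10: "subjects will have been on a constant dose of bimekizumab 160mg or 320mg for at least 36 weeks prior to AS0009 entry".
- SAP 10.2: in the summaries combining both studies, events up to 140 days after the last AS0009 dose go to 160 mg. Events on the day of a switch go to the previous dose, apart from four exception types.

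**The concern.** The three column labels are the ones used in the SAP's genuine by-dose tables, so a reader will take the columns as like for like. They are not. For 320 mg the count is close to a point prevalence: how many subjects still had an unresolved event when AS0009 began. For 160 mg it is mainly a cumulative incidence over about four years. Dividing both by everyone who received the dose removes neither difference.

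The effect is strongest for short events. An infection on 320 mg that cleared before entry is absent from the table, while the same infection on 160 mg during AS0009 is counted. Long-term safety is the primary objective, and SAP 4.3 schedules every output except the COVID-19 ones for the Week 108 interim as well, so the table belongs to both deliveries. It also sits poorly with SAP 3.10, which says that safety displays drawing on AS0008 will take AS0008 exposure into account.

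**Working it through.** The plan gives no figure for this table, so there is nothing to reproduce. The check has two parts.

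**What can enter each column**

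- 320 mg: AS0008-onset events on 320 mg that continued past the first AS0009 dose. If the switch-day rule applies here, first-day AS0009 events in subjects coming from 320 mg are added, except the four exception types. That is about one day of risk.
- 160 mg: AS0008-onset events on 160 mg that continued, plus all other AS0009-onset events. The window is up to 204 weeks plus 140 days (20 weeks), 224 weeks in all.
- Denominators: every Safety Set subject receives 160 mg in AS0009, so the 160 mg denominator is the whole Safety Set. It includes subjects who had no 160 mg in AS0008 and could not have carried over a 160 mg event. The 320 mg denominator is only those given 320 mg in AS0008.

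**How large the built-in gap could be**

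Inputs from the documents are 320 mg exposure of 36 weeks (switch at AS0008 Week 12) or 48 weeks (320 mg throughout), and 160 mg time at risk of up to 224 weeks. The event rate L (the same on both doses), the mean duration D and constant-rate Poisson occurrence are assumptions.

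- 160 mg column: 1 − exp(−L × T160)
- 320 mg column: 1 − exp(−L × D × (1 − exp(−T320/D)))

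Times are converted to years. Carried-over 160 mg events are left out, which understates the gap.

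| L per year | Mean duration | 160 mg, 224 weeks | 320 mg, 36 to 48 weeks |
|---|---|---|---|
| 0.05 | 2 weeks | 19.3% | 0.2% |
| 0.05 | 8 weeks | 19.3% | 0.8% |
| 0.05 | 26 weeks | 19.3% | 1.9% to 2.1% |
| 0.05 | never resolves | 19.3% | 3.4% to 4.5% |
| 1 | 2 weeks | 98.6% | 3.8% |
| 1 | 8 weeks | 98.6% | 14.1% to 14.2% |
| 1 | 26 weeks | 98.6% | 31.2% to 34.3% |
| 1 | never resolves | 98.6% | 49.8% to 60.1% |

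With a shorter 108 weeks on 160 mg, L = 0.05 and 8-week events, the result is 9.8% against 0.8%. The gap closes only for very frequent events that never resolve: at L = 2 it is 74.8% to 84.1% against 100.0%.

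For a single preferred term at 0.10 per year and an assumed mean of 3.5 years at risk in AS0009:
- 160 mg: 1 − exp(−0.10 × 3.5) = 29.5%
- 320 mg, 14 days: 1 − exp(−0.10 × 14/365.25) = 0.38%
- 320 mg, 30 days: 1 − exp(−0.10 × 30/365.25) = 0.82%

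The never-resolving rows are also what the 320 mg column would show if every 320 mg event were counted but left as a crude percentage. At L = 0.05 that raises 0.8% to 3.4% to 4.5%, still well short of 19.3%. The inclusion rule and the unequal window both contribute.

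With all 320 mg events counted and exposure adjusted, the gap goes. In a simulation with equal rates (285 subjects over 224 weeks, against an assumed 140 over 40 weeks), EAIR per 100 patient-years was 5.0 and 5.0 at L = 0.05, and 100.2 and 100.7 at L = 1.

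**The case against.** The best defence is that the table is an inventory. SAP 10.2 calls it additional, and it shows which events were present during AS0009, with onset dose as an attribute. The study is single-arm and no comparison from this table is planned. An EAIR mixing carried-over with new events would have no coherent time at risk, so n and % may be deliberate. All of that is fair. The missing EAIR is not the fault in itself. The fault is pooling two kinds of event in one row under dose columns, without a caution.

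The objection also limits the point. A reader might infer that the plan loses 320 mg events, or that its by-dose safety reporting as a whole is biased. The documents do not support that. SAP 10.2 also specifies all-TEAE and serious-TEAE tables for AS0008 and AS0009 by dose at onset, with EAIR and EAER. They include 320 mg events that had resolved. SAP 10.2.2 uses dose-specific time at risk, and the AE listings cover both studies apart from placebo-onset events.

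Nor is this the only by-dose display without exposure adjustment: the combined AS0008 and AS0009 TEAE overview is also specified as number and percentage only. It does, however, apply one inclusion rule to every column.

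The magnitudes can be challenged too. Rates, durations and the 3.5 years are not in the documents, and variation between subjects would lower the highest 160 mg percentages. The size is therefore illustrative.

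**Conclusion.** The point stands for this one table. Its 160 mg and 320 mg percentages are not comparable, and the direction (320 mg lower) follows from the counting rules under equal true rates. At the assumed rate of 0.10 per year the example gives about 0.4% to 0.8% against 30%; other plausible inputs give anything from a modest gap to a very large one. It would be wrong to say that the 320 mg column holds nothing but carried-over events, because switch-day events can enter it, or that the primary and secondary safety variables are affected. This is a correction to a supplementary descriptive table that should be made; it does not undermine the main safety analysis.

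**What to change.** Do not pool the two event types in one row. Re-specify the table in SAP 10.2 as two blocks:

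- (a) TEAEs ongoing from AS0008 at AS0009 entry, by dose at onset. Limit each column's denominator to Safety Set subjects who received that dose in AS0008. Count events begun on other bimekizumab doses (16 mg, 64 mg) in BKZ Total only, and keep placebo-onset events excluded as now. Under the planned sequences in SAP 3.7 both dose columns then have the same rule and the same possible AS0008 exposure of 36 or 48 weeks.
- (b) TEAEs with onset in AS0009, by treatment group at completion of AS0008 and overall.

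Add a footnote that dose comparisons are to be made from the EAIR and EAER tables. The footnote alone would be cheaper, but it would leave a pooled row with no clear meaning.

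The cost is a wording change and one re-specified table, with no new data. Block (b) partly repeats the all-TEAE table by treatment group at completion of AS0008 that is already planned.

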10.2.1 Adverse event duration and time since first/last dose

Missing start or end dates will be imputed as described in [Section 4.2.2](#) prior to any calculation described in this section.

The duration of each AE will be calculated as follows:

$$\text{Duration (days)} = \text{date of outcome} - \text{date of onset} + 1 \quad (15)$$

The time since first bimekizumab dose for each TEAE will be calculated three times for each of the reference dates below:

- Relative to the date of first administration of bimekizumab in AS0008.
- Relative to the date of the first dose of bimekizumab 160mg, only for AEs with onset during treatment with bimekizumab 160mg OR
- Relative to the date of the first dose of bimekizumab 320mg, only for AEs with onset during treatment with bimekizumab 320mg.
 - For these criteria during treatment refers to TEAEs with onset up to 140 days after the last dose on that treatment.
- Relative to the start date of study medication in AS0009.

Time since first dose will be calculated as follows for AEs occurring on or after the reference date (as defined above):

$$\begin{aligned} \text{Time since first BKZ dose (days)} \\ = \text{Date of AE onset} - \text{Reference date} + 1 \end{aligned} \quad (16)$$

The time since most recent bimekizumab dose for each TEAE will be calculated as follows for AEs occurring on or after the reference date (as defined above):

$$\begin{aligned} \text{Time since most recent BKZ dose (days)} \\ = \text{Date of AE onset} \\ - \text{Date of most recent dose prior to AE} + 1 \end{aligned} \quad (17)$$

For any AE occurring on the same day as a given dosing occasion the most recent dose will be considered to be the dose given on the same day i.e., time since most recent dose would be equal to 1 for all such AEs.

For AEs occurring prior to the reference date (as defined above) the time since dosing will be calculated as follows for first/most recent BKZ dose:

$$\text{Time since BKZ dose (days)} = \text{Date of AE onset} - \text{Reference date} \quad (18)$$

Days on treatment at AE onset will be calculated three times using the same three reference dates as for time since first dose. Days on treatment at AE onset will be calculated as:

$$\begin{aligned} \text{Days on treatment at AE onset} \\ = \text{Date of last or latest dose prior to AE onset} \\ - \text{Reference date} + 1 \end{aligned} \quad (19)$$

As above, for any AE occurring on the same day as a given dosing occasion the last or latest dose prior to AE onset will be considered to be the dose given on the same day as the event.

For AEs occurring prior to the reference date, the days on treatment will be 0.

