Exposure Category	Start date	End date	Duration of Exposure
Total exposure to BKZ 160mg	First dose of BKZ 160mg in AS0008 or AS0009	Last dose of BKZ 160mg in AS0009	Minimum of [(End date – start date + 140 ^a) +1] and (Date of last clinical contact ^b – start date + 1)
Exposure to BKZ 320mg	First dose of BKZ 320mg in AS0008	First dose of BKZ 160mg in AS0009 for subjects who were dosed in AS0009 ^c . Last dose of BKZ 320mg in AS0008 for subjects who were not dosed in AS0009	(End date – start date + 1) for subjects who were dosed in AS0009. Minimum of [(End date – start date + 140 ^a) +1] and (Date of last clinical contact ^b – start date + 1) for subjects who were not dosed in AS0009
Exposure to BKZ 160mg in AS0009	First dose of BKZ 160mg in AS0009	Last dose of BKZ 160mg in AS0009	Minimum of [(End date – start date + 140 ^a) +1] and (Date of last clinical contact ^b – start date + 1)
Subjects who died ^d	Start date for each option as above	Date of death	End date – start date + 1

BKZ=bimekizumab.

^a 140 days refer to 5 half-lives of BKZ.^b Date of last clinical contact for each subject is defined as the maximum of [last visit date including SFU visit (including unscheduled SFU visits), last AE start date (including imputed AE start dates), date of study termination or completion, last date of study drug administration following rules for partial treatment end dates as per Section 4.2.4].^c In the event that the first dose in AS0009 was more than 140 days after the last dose in AS0008, the exposure time at risk for 320mg will be calculated using AS0008 end date – AS0008 start date + 140 days.^d For subjects who died, the date of death will be used to replace the end date in the calculation of exposure time at risk only if the subject died within the ‘at risk’ interval (i.e., within 140 days following the last dose [not applicable for duration on BKZ 320mg] or if the subject died before dosing in AS0009 (for time at risk on BKZ 320mg). If the subject died more than 140 days after the last dose of BKZ in AS0009 the exposure time at risk will be calculated using the ‘at risk’ interval of 140 days. Note that date of death should be equivalent to date of last clinical contact.

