Summaries of AEs in AS0008 and AS0009 will include AEs with onset on the first dose of bimekizumab in AS0008 up to 140 days after the last dose of bimekizumab in AS0009. AEs which occur on the day of a treatment switch will be considered to have begun on the previous treatment, with the exception of the following AEs which will be considered to have begun on the new treatment:

- Events that fulfill the anaphylaxis criteria for acute events (see [Section 10.2.3](#)).
- Events that fulfill the hypersensitivity reaction criteria for (see [Section 10.2.3](#)).
- Events with a HLT of “Administration site reactions NEC”.
- Events with an HLT of “Injection site reactions”.

AEs which occur on the first day of bimekizumab treatment in AS0008 following initial treatment with placebo will not be included in the summaries, unless they fulfill 1 of the 4 exception criteria above. AEs which occur after the last dose of bimekizumab in AS0009 and up to 140 days after the last dose of bimekizumab in AS0009 will be assigned to bimekizumab 160mg.

AEs will be presented as “number of subjects (percentage of subjects) [number of events]”. “[number of events]” will include all cases of an AE including repeat occurrences in individual subjects, while “number of subjects” will count each subject only once.

An overview of TEAE (number and percentage of subjects with any TEAE, serious TEAE, TEAE leading to study discontinuation, TEAE leading to permanent withdrawal of study medication, drug-related TEAE, severe TEAE, fatal AE [see note below], fatal TEAE and TEAE with missing seriousness) will be provided by treatment group at completion of AS0008 and overall. This summary will be repeated by SS Sub-population. It will also be repeated including all TEAEs in AS0008 and AS0009 reported for subjects in the AS0009 SS (with the exception of those with onset during placebo treatment) combined.

The category for fatal AEs will be based on all subjects enrolled in AS0009 in all the above summaries.

The following categories of TEAE will be summarized by MedDRA SOC, HLT and PT, including EAIR and EAER (calculated as described in [Section 10.2.2](#)), where all summaries refer to AEs reported in AS0009 only except where stated:

- All TEAEs by treatment group at completion of AS0008 and overall.
- All TEAEs by treatment group at completion of AS0008 and overall, by SS Sub-population.
- Serious TEAEs by treatment group at completion of AS0008 and overall.

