10.2.2 Exposure-adjusted incidence rate and exposure-adjusted event rate

The time at risk (in days) at AE onset is the same as the time since first bimekizumab dose as described in [Section 10.2.1](#).

Total time at risk (as defined in [Section 10.1](#)) and time at risk at AE onset will be divided by 365.25 to give years at risk.

EAIR and EAER will be calculated separately for tables including all events in AS0008 and AS0009 combined, and for tables including events with onset in AS0009 only. The former tables will use time at risk relative to the start date of bimekizumab 160mg or 320mg (for the ‘BKZ 160mg’ and ‘BKZ 320mg’ columns) and time at risk relative to the date of the first dose of bimekizumab (for the ‘BKZ Total’ column). The latter table will use time at risk relative to the start date of study medication in AS0009.

The EAIR is defined as the number of subjects with a specific AE adjusted for the exposure and will be scaled to 100 patient-years:

$$\frac{EAIR = 100 * n_{AE}}{\sum_{i=1}^{n_{AE}} T_{Exp,i} + \sum_{j=1}^{n_{noAE}} T_{Risk,j}} \quad (20)$$

Where n_{AE} is the number of subjects with the AE, $T_{Exp,i}$ is a subject’s time at risk at AE onset in years (equation [15] in years) and $T_{Risk,j}$ is the time at risk in years for subjects who did not experience the AE of interest.

If a subject has multiple events at the level of coding evaluated, the time at risk at AE onset is calculated to the first occurrence of the AE.

Exact Poisson 95% CIs for incidence rates are calculated using the relationship between the Poisson and the chi-square distribution (Ulm, 1990; Fay and Feuer, 1997):

$$LCL = \frac{\chi^2_{2n,\frac{\alpha}{2}}}{2} \quad (21)$$

$$UCL = \frac{\chi^2_{2(n+1),1-\frac{\alpha}{2}}}{2} \quad (22)$$

$$CI_{Lower} = 100 * \frac{LCL}{\sum_{i=1}^{n_{AE}} T_{Exp,i} + \sum_{j=1}^{n_{noAE}} T_{Risk,j}} \quad (23)$$

$$CI_{Upper} = 100 * UCL \frac{UCL}{\sum_{i=1}^{n_{AE}} T_{Exp,i} + \sum_{j=1}^{n_{noAE}} T_{Risk,j}} \quad (24)$$

where n_{AE} is the number of subjects with the AE and is the basis for the number of the degrees of freedom for the chi-square quantile for the upper tail probability χ^2 , $T_{Exp,i}$ is a subject's time at risk at AE onset in years, n_{noAE} the number of subjects without the specific AE and $T_{Risk,j}$ the total time at risk for subjects who did not experience the AE.

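### SAP 10.2.1 extends onset during 320 mg treatment to 140 days after the last 320 mg dose with no cut at the switch to 160 mg, which conflicts with Table 10-2 and the onset rules in Section 10.2

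*SAP*

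**What the plan says.** Four parts of the SAP bear on this.

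- **Section 10.2.1** derives timing variables for AEs. It opens with "The time since first bimekizumab dose for each TEAE will be calculated three times for each of the reference dates below", then lists four reference dates. Two are dose-specific (first 160 mg dose, first 320 mg dose). They are joined by OR, and each is limited to events arising during treatment with that dose. The limiting sentence is "For these criteria during treatment refers to TEAEs with onset up to 140 days after the last dose on that treatment".
- **Section 10.1, Table 10-2** gives time at risk. For 320 mg the end date is "First dose of BKZ 160mg in AS0009 for subjects who were dosed in AS0009", and the duration is end minus start plus 1. Footnote a says "140 days refer to 5 half-lives of BKZ". Footnote c covers a long gap between studies: "In the event that the first dose in AS0009 was more than 140 days after the last dose in AS0008", 320 mg time is taken to 140 days past the AS0008 end date instead.
- **Section 10.2** handles the change of dose: "AEs which occur on the day of a treatment switch will be considered to have begun on the previous treatment". Four kinds of acute event are excepted and go to the new treatment. Events in the 140 days after the last AS0009 dose go to 160 mg. The planned outputs include "All TEAEs in AS0008 and AS0009 by treatment at time of AE onset (BKZ 160mg, BKZ 320mg and BKZ Total"), with a matching table for serious TEAEs.
- **Section 10.2.2** defines the rates. For the combined tables, "The former tables will use time at risk relative to the start date of bimekizumab 160mg or 320mg" in the two dose columns. Time at risk at AE onset is taken from 10.2.1. The EAER numerator runs to 140 days after the last dose, without saying which treatment's last dose. For T_Exp the text cites equation 15, which is AE duration; equation 16 is time since first dose.

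**The concern.** All eight treatment sequences in SAP Section 3.7 end on 160 mg, so every subject who contributes to the 320 mg column of the combined tables changes dose at AS0009 entry. For such a subject, an AE at AS0009 Week 8 satisfies both dose-specific conditions in 10.2.1. Table 10-2 has already stopped the 320 mg clock, and the switch-day rule in 10.2 implies that the event belongs to 160 mg.

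The 10.2.1 sentence cannot be dismissed as inert text. It is the only place where the SAP says explicitly what onset during treatment with a given dose means, and 10.2.2 draws T_Exp for the EAIR from that section.

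Safety is the primary objective, and the combined tables are where AE rates are shown by dose at onset. Two programmers, one following 10.2.1 and one following 10.2, could produce different 320 mg columns.

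**Working it through.** **1. The plan's own figure.** Table 10-1 equates 28 days with one half-life, so 5 x 28 = 140 days, which is also 20 weeks x 7. The 140-day window reproduces.

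**2. Inputs.**
- Time on 320 mg: 48 weeks for subjects on 320 mg from the start of AS0008, and 36 weeks for those who changed to it at Week 12 (sequences in SAP 3.7).
- Time at risk by Table 10-2 (end - start + 1): T = 36 x 7 + 1 = 253 days, or T = 48 x 7 + 1 = 337 days.
- Gap from last 320 mg dose to first 160 mg dose: assumed 28 days, the dosing interval in SAP 3.2.2.
- Also assumed: a constant event rate before and after the switch, and no dropout.

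**3. Overlap after the switch.** W = 140 - 28 = 112 days. During these days both dose-specific conditions in 10.2.1 hold.

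**4. One subject.** Take 48 weeks on 320 mg and an AE at AS0009 Week 8 (Day 57). Measured from the first 320 mg dose, time at onset is 336 + 57 = 393 days. Table 10-2 gives that subject 337 days of 320 mg time at risk in total. T_Exp would exceed the subject's whole time at risk, which shows that the two texts cannot both apply.

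**5. EAER if 10.2.1 governed assignment.** Ratio to the true rate = (T + W)/T.
- 36 weeks: 365/253 = 1.44
- 48 weeks: 449/337 = 1.33

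The gap matters moderately. If it were 21 or 35 days (the limits that Protocol 7.2 allows between AS0009 doses), W would be 119 or 105 days. The excess would be 119/253 = 47% or 105/253 = 42% at 36 weeks, and 119/337 = 35% or 105/337 = 31% at 48 weeks.

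**6. EAIR if 10.2.1 governed assignment.** Cases are followed to S = T + W and non-cases to T. With event rate r per day:

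EAIR = [1 - exp(-rS)] / {[1 - exp(-rS)]/r - W exp(-rS)}

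| True rate per 100 patient-years | 36 weeks on 320 mg | 48 weeks on 320 mg |
|---|---|---|
| 5 | 7.14 (x1.43) | 6.60 (x1.32) |
| 20 | 27.7 (x1.38) | 25.6 (x1.28) |
| 100 | 121.8 (x1.22) | 114.5 (x1.15) |

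**7. Under the onset rule of 10.2.** Numerator and denominator both stop at the switch. The EAER ratio is T/T = 1.00, the EAIR equals the true rate, and each event falls in one dose column only.

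**The case against.** The strongest reply is that 10.2 places events in columns, and 10.2.1 only derives a time variable. The combined tables are by treatment at onset. The switch-day rule would serve no purpose if 320 mg kept every event for 140 days after its last dose. Within 10.2.1, three calculations for four listed dates works only if the OR makes 160 mg and 320 mg a single reference per event. The 140-day limit also has a sensible use as a cap when the gap between studies is long, as in footnote c of Table 10-2 and the rule on non-treatment-emergent events in 10.2.

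Most of this stands. A reader might infer that the 320 mg rates are inflated and that events are counted twice. The documents do not support that, because it follows only if 10.2.1 overrides the onset rule. Nor is it double-counting of events that a subject who took 320 mg appears in all three columns: SAP 3.7 provides for that.

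The reply does not settle the text. Section 10.2 does not define treatment at time of onset beyond the switch day and the tail after the last AS0009 dose. For about 112 days both 10.2.1 conditions are true, and OR does not say which prevails. The EAER definition leaves the relevant last dose open, and the T_Exp reference points to the wrong equation.

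**Conclusion.** This is a wording conflict with a conditional effect. The 10.2.1 window lacks a cut at the change of dose and, as written, disagrees with Table 10-2 and with what 10.2 implies. Read as probably intended, by treatment at onset, nothing is biased.

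If the sentence were programmed literally, the 320 mg EAER would be about 33-44% too high and the EAIR about 15-43% too high for true rates between 100 and 5 per 100 patient-years. These sizes rest on the 28-day gap, constant rate and no dropout assumed above; they are not figures from the documents.

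The reach is narrow. The rates at issue are in the 320 mg column of the combined tables of all and of serious TEAEs by treatment at onset. The further table in 10.2 by treatment at onset carries counts and percentages only. AS0009-only tables measure time from the AS0009 start and are unaffected, as is BKZ Total.

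**What to change.** 1. In SAP 10.2.1, end the window for each dose at the earlier of two dates: 140 days after the last dose on that treatment, and the first dose of the next treatment. Keep the switch-day rule and its four exceptions by reference to Section 10.2. This agrees with Table 10-2, including footnote c.
2. In the EAER definition in 10.2.2, state that events in the by-dose columns are counted by the same treatment-at-onset rule.
3. In 10.2.2, change the reference for T_Exp from equation 15 to equation 16.

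The cost is a few sentences in the SAP and one check that the programmed treatment-at-onset derivation stops 320 mg at the switch. No new data or outputs are needed.
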